4.8 Data Analysis

Protocol #: 18-2513

PI: [name]

Version date: 07/01/2019

Univariate comparisons between various measures will be compared between the fluid responder and non-responder groups using t-tests or Fisher's exact test for continuous and categorical measures, respectively. Area under the curve will be calculated for CI and CRI using both simple logistic regression models including no confounders and multiple logistic regression models including confounders. Confounders will be identified for inclusion in the multiple logistic regression models by calculating the univariate association with the gold standard (using a $p < 0.10$ threshold). These adjusted models will be used to verify thresholds for classification using CI and CRI which will then be applied to calculate classification summary measures (e.g., PPV, NPV, sensitivity, and specificity). Data analysis will be performed by a biostatistician funded by the Division of Pediatric Surgery using R and SAS statistical software programs.

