non-responders for Δ VPeak was 0.94 [18]. While the optimal Δ VPeak varied from 7-20% among studies, one of the larger series using a Δ VPeak of 10% as a threshold found the sensitivity and specificity to be 100% in distinguishing fluid responders based on aortic velocity-time integrals identified by transthoracic echocardiogram [7]. Based on these results, we plan to define fluid responders as those who have $>10\%$ Δ VPeak between pre- and post-fluid challenge.

Bedside evaluation of the IVC to calculate the CI is a commonly used tool in adults [19, 20]. It serves as a surrogate to measure preload variation induced by mechanical ventilation. The technique requires limited ultrasonographic experience often at the critical care or anesthesia fellow level. In pediatrics, the predictive utility of IVC CI has only been evaluated in small series with conflicting results [21].

The CRI is another non-invasive devise using a photoplethysmographic probe (CipherOx-CRI) placed on the index finger. Based on data gathered from the probe, a computer-generated algorithm is then used to calculate a number between zero and one, referred to the CRI (Figure 3) [22]. The CRI correlates to one's intravascular volume status and proximity to hemodynamic collapse [23].

Figure 3

Legend: CRI, compensatory reserve index. CRI=1 is normovolemia and CRI=0 is the point at which the patient is at highest risk for hemodynamic decompensation.

Confounding factors that can influence dynamic measurements must also be considered. For instance, cardiac arrhythmias, small tidal volumes, spontaneous respiration, and high positive end-expiratory pressure have been found to decrease the predictive utility of pulse pressure variability and IVC CI [24-26]. Thus, it is paramount to use and apply these measurements in the appropriate clinical setting. Presumably, the influence confounding variables have on the predictive utility of these indices in children is similar to that of adults, however, comparative analyses have not been performed. Thus, when interpreted in the appropriate clinical context, these minimally and non-invasive devices are tools available to guide a balanced fluid resuscitation; however, while small series exist in various pediatric populations, validation is necessary in order to apply these tools in hypovolemic children with significant blood loss.

Protocol #: 18-2513

PI: [name]

Version date: 07/01/2019

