Hypothesis II: CRI and collapsibility index will reliably predict fluid responsive patients with an approximate area under the receiver operating characteristic curve (AUROC) of 0.9 while other indices will have a lower predictive accuracy.

Aim III: Evaluate confounding variables that may influence predictive measures outlined in Aim II.

Hypothesis III: Confounding variables that may decrease the predictive accuracy of indices described in Aim II include spontaneous breathing over the ventilator, minimal blood loss, and hypothermia

4. Materials and Methods:

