4.4 Definitions

- *Bolus* – 10 - 20 ml/kg fluid (isotonic crystalloid, colloid, or blood product) up to 1 L and given within a 10 minutes period
- *Fluid responders* – Children who have a pre- and post-fluid challenge $\Delta VPeak > 10\%$ calculated using the equation ($\Delta VPeak_{pre} = (VPeakmax_{pre} - VPeakmin_{pre}) /$

Protocol #: 18-2513

PI: [name]

Version date: 07/01/2019

$$[(V_{peakmean_{pre}})] - (\Delta V_{Peak_{post}} = (V_{Peakmax_{post}} - V_{Peakmin_{post}}) / [(V_{peakmean_{post}})] \times 100$$

- *Multiple fluid challenges* – If more than one fluid bolus is administered at least 30 minutes apart, they will be reported as individual events
- *Pre-bolus measurements* – Hemodynamic measurements will be calculated or recorded three times thirty seconds apart and averaged just before a bolus is administered. Cine loops from IVC measurements will be recorded three times, thirty seconds apart for post-hoc CI calculation. Peak aortic velocity and CRI will be recorded on the EDM monitor and averaged over 90 seconds.
- *Post-bolus measurements* - Hemodynamic measurements will be calculated or recorded three times and averaged five minutes after a bolus is completed. These measurements will be time and repeated in an identical fashion to pre-bolus measurements.

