4.9.2 CardioQ-EDM Contraindications

- Doppler probes (DP240 and I2n) should not be placed in patients under 16 years of age. We will be using the KDP72 probe
- Do not use where nasal injuries are apparent or may have occurred.
- Do not use where nasal polyps exist.
- Do not use where there are circumstances of facial trauma.
- Do not use where there is a risk of brain injury.
- Do not use in patients undergoing intra-aortic balloon pumping.
- Do not use with carcinoma of the pharynx, larynx or esophagus.
- Do not use with aneurysms of the thoracic aorta.
- Do not use with tissue necrosis of the esophagus or nasal passage.
- Do not use in close proximity to laser surgery.
- Do not use in patients with pharyngo-oesophago-gastric pathology and/or severe bleeding diatheses.

5. Specific Aims:

Aim I: Define fluid responders based on aortic ΔV_{peak} : Among infants undergoing cranial vault reconstruction for craniosynostosis, we aim to determine the proportion who respond to clinically administered fluid or blood products defined by pre- and post-fluid challenge EDM $\Delta V_{Peak} >10\%$.

Mock-up Table 1: Demographics of Responders and Non-Responders to Initial 10 mL/kg bolus prior to surgical incision

Variable	Responders	Non-Responders	P-value
Demographics			
Age			
Weight			
Height			
BMI			
Gender			
Ethnicity			
Duration of NPO status			
Associated syndrome			

Legend: BMI, body mass index; npo, nil per os

Aim II: Calculate the PPV, NPV, sensitivity, specificity, and optimal threshold for CRI and collapsibility index as tools to prediction fluid responder

Protocol #: 18-2513

PI: [name]

[figure not shown]
Version date: 07/01/2019

		Fluid Responsive	
		Yes	No
CRI Threshold	+	True Positive	False Positive
	-	False Negative	True Negative

		Fluid Responsive	
		Yes	No
CI Threshold ($\geq 15\%$)	+	True Positive	False Positive
	-	False Negative	True Negative

Performance will also be calculated for heart rate, systolic blood pressure, mean arterial pressure, pulse pressure variability and stroke volume variability. Two separate analyses will be performed – one for the 10 ml/kg protocolized bolus provided immediately after induction and one accounting for all boluses provided.

Mock-up Figure

Mock-up Table 2 – Performance at predicting fluid responsiveness

Variable	Correlation (r)	AUC
IVC CI		
CRI		
SBP		
PPV		
SVV		
MAP		
HR		

Protocol #: 18-2513

PI: [name]

Version date: 07/01/2019

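### Section 4.8 uses the fall in ΔVPeak only as a >10% label, gives no method for the Correlation (r) in Mock-up Table 2, and plans no paired comparison of CRI or CI with the current indices

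*Combined protocol and SAP*

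**What the plan says.** Section 4.4 computes ΔVPeak before and after the bolus, takes the difference, and then cuts it: responders are "Children who have a pre- and post-fluid challenge" difference above 10%. The background gives the reason for the cut. It cites a meta-analysis with a summary AUROC of 0.94, notes that the best cut "varied from 7-20% among studies", describes one larger series that used 10%, and concludes "Based on these results, we plan to define fluid responders as those who have" more than 10%.

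Section 4.8 names three kinds of analysis:

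- Group comparisons: "Univariate comparisons between various measures will be compared between the fluid responder and non-responder groups using t-tests" (or Fisher's exact test).
- Accuracy: "Area under the curve will be calculated for CI and CRI using both simple logistic regression models including no confounders", and again with confounders.
- Covariate selection for those logistic models, by "calculating the univariate association with the gold standard" at p < 0.10.

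Gold standard is not defined in that section, but the logistic models imply the yes/no label.

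Section 5 goes further. Aim II adds performance measures for heart rate, SBP, MAP, PPV and SVV. Mock-up Table 2, "Performance at predicting fluid responsiveness", has a Correlation (r) and an AUC column for all seven indices. The Aim III table lists multivariable linear regression with the indices or their AUROC as outcome.

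Hypothesis II expects an AUROC of about 0.9 for CRI and CI, "while other indices will have a lower predictive accuracy". The stated study goal is to replace arterial lines if CRI or CI predicts at least as well as the indices now in use.

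**The concern.** Two gaps meet here.

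First, the central claim is comparative, yet nothing in Section 4.8 compares one index with another. Seven AUCs side by side, with no interval for any difference, cannot show that CRI or CI is better than, or as good as, pulse pressure variability. All indices are measured on the same children, so the comparison has to be paired.

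Second, the reference quantity enters Section 4.8 only after it has been cut. A child whose fall is 10.5 counts the same as one whose fall is 30, and children at 9.5 and 10.5 count as opposites. Sensitivity, specificity, PPV and NPV need a cut. Asking which index tracks the response more closely does not. The r column suggests that such an analysis was wanted, but as written it could hold a correlation with the label, with the continuous fall, or with the baseline ΔVPeak.

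At stake is a study of this size reporting no difference between indices when it had little chance of seeing one, or claiming an advantage from AUC estimates whose difference was never assessed.

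**Working it through.** The text available for review states no sample size, power or main-test alpha, so there is no figure of the plan's own to reproduce.

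**Inputs**
- Children: 30 CardioQ-EDM probes (Section 4.2), each for a single patient (Section 4.9.1). This is a supply figure, used here as an assumption.
- Responder share: about half for the post-induction bolus (Hypothesis Ia), so the cut falls near the median.
- AUC of CRI or CI: 0.90 (Hypothesis II).
- Comparator AUC: not stated. The range 0.70, 0.75, 0.80 is assumed.
- Assumed model: bivariate normal data, one bolus per child, independent index errors, ΔVPeak measured without error.

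**Step 1. Information kept by the cut.** For a moderate association and responder share p with cut point c, the fraction kept is φ(c)²/[p(1−p)]. At p = 0.5 this is 2/π = 0.637, and 30 × 0.637 ≈ 19, so 30 children carry the information of about 19. At a 70/30 split it is 0.576, and 30 × 0.576 ≈ 17.

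**Step 2. One index tested alone.** AUC 0.90 corresponds to a standardised difference √2 × z(0.90) = 1.812. A two-sided 5% t-test with 15 per group then has 99.9% power, so the label costs almost nothing here.

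**Step 3. Comparing two indices.** The fall is drawn as standard normal and cut at its median. Index correlations with the fall are set to give the required AUC: 0.83 for 0.90, 0.64 for 0.80, 0.54 for 0.75 and 0.44 for 0.70. Both methods use a bootstrap 95% interval for the paired difference, resampling children, and differ only in the measure compared.

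| Comparator AUC | Power, rank correlation with the fall | Power, AUC on the label | Gain |
|---|---|---|---|
| 0.70 | 69% | 47% | 69 − 47 = 22 |
| 0.75 | 52% | 34% | 52 − 34 = 18 |
| 0.80 | 29% | 21% | 29 − 21 = 8 |

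These are simulated values. Repeat runs gave 68–69%, 49–54% and 30–31% for the rank version, and 49%, 34% and 24% for the AUC version, so each gain is uncertain by a few points. The false-positive rate of the rank bootstrap was about 4% when the indices were truly equal, so the gain does not come from inflated error.

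**Step 4. Does the gain survive another shape?** CRI is bounded between 0 and 1 and could flatten at large responses. Let the better index follow tanh of the fall plus noise, with its true AUC held at 0.90:

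| Comparator AUC | Rank correlation | AUC on the label |
|---|---|---|
| 0.70 | 51% | 48% |
| 0.75 | 35% | 36% |
| 0.80 | 14% | 19% |

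With steeper flattening, tanh of twice the fall, it was 30% vs 45% (comparator 0.70) and 19% vs 32% (0.75). The advantage depends on the index continuing to rise or fall with the size of the response.

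**The case against.** The strongest reply is that Aim II and Hypothesis II concern AUROC for a response above 10%, that the bolus decision is itself yes or no, and that correlation with the size of the fall is a different estimand. This stands. Step 4 shows that the two can rank indices differently, so the correlation can support the AUC comparison but cannot replace it.

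A reader might also infer several stronger things that the documents do not support:

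- *That the whole plan is dichotomised.* This is true of Section 4.8 only. Section 5 has the r column and the Aim III linear regression, although that regression does not model the ΔVPeak response.
- *That the planned tests lose most of their power.* A single index at AUROC 0.9 loses almost nothing (Step 2). The loss concerns moderate associations and comparisons between indices.
- *That the comparison falls from about 84% to 45% power.* Those values arise at comparator AUC 0.70 from a Williams test on raw values against a DeLong test on the label. The plan names neither. The DeLong test also rejected only about 2% of the time when both AUCs were 0.90, so part of that gap is its conservatism. The like-for-like figures are those in Step 3.
- *That the covariate screen should also use the continuous fall.* Its purpose is to choose covariates for logistic models whose outcome is the label. Screening on another outcome would not match those models. A more sensitive p < 0.10 screen would also admit more of roughly 20 candidates to models with about 15 responders. The screen is best left as it is.
- *That the trial has at most 30 children.* Thirty is a probe count, and some pages were not available for review. The all-bolus analysis may hold more events, though correlated ones.
- *That the 10% cut is arbitrary.* It is fixed in advance, and the background draws it from both a meta-analysis and a series.

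**Conclusion.** The point holds as a gap in specification with a moderate cost in efficiency. Section 4.8 uses the continuous fall only as a label, r is undefined and has no method, and the comparison on which the study goal rests is not planned. Under normality, with about 30 children, half responders and AUC 0.90 for CRI or CI, adding the continuous comparison raises power by roughly 8 to 22 points, depending on the comparator. The gain is conditional: it disappears or reverses if the better index saturates. It also does not make the study well powered. Even the better column in Step 3 runs from 29% to 69%, so an interval that includes zero should not be read as equivalence of the indices. The 10% label is not itself an error and is needed for Aims I and II.

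**What to change.** Keep the >10% label for Aim I, for sensitivity, specificity, PPV, NPV and AUC, and for the covariate screen that feeds the logistic models.

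Add to Section 4.8, for the protocolized post-induction bolus:

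1. The paired difference in AUC between CRI and each current index, and between CI and each current index, with a bootstrap 95% interval resampling children.
2. As a supporting analysis, the rank correlation of every index with the continuous fall in ΔVPeak (pre minus post, as computed in Section 4.4), with the same paired differences in absolute rank correlation and the same type of bootstrap interval.
3. A sentence saying that the correlation measures something other than AUROC at 10%, that it may favour a different index if one flattens at large responses, and that the AUC comparison leads.

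In Mock-up Table 2, define r as this rank correlation and add the two paired differences.

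The cost is a few sentences and a few lines of code. No new data, procedures or patients are needed. The price is a second accuracy measure that clinicians will find less direct than the AUC, which is why it is reported beside the AUC.

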While numerous tools are available to guide resuscitation, one potential benefit of this project is to validate the use of CipherOx-CRI in this cohort. If CRI proves to be a valuable predictor of intravascular volume status and the need for volume expansion, this could negate the need for arterial line placement which is time consuming, invasive, and associated with complications such as arterial thrombosis. Furthermore, after validation in this cohort, additional studies could be performed in other groups of children at risk for hemorrhagic shock in the hopes to guide ongoing resuscitation accurately without the need for invasive devices.

3. Specific Aims and Hypotheses:

Aim I: Among infants undergoing cranial vault reconstruction for craniosynostosis, we aim to determine the proportion who respond to clinically administered fluid or blood products defined by pre- and post-fluid challenge $\Delta V_{Peak} > 10\%$.

Hypothesis Ia: We hypothesize that approximately half of the cohort will be fluid responsive defined by ΔV_{Peak} by $> 10\%$ after a 10 mL/kg fluid bolus is administered immediately following induction. Although this is a prediction, it is based on previous published reports suggesting a relatively even distribution among patients who clinicians believe need volume expansion. Additionally, because these children have a mean weight of 6.4 kg and will have been nil per os for several hours prior to surgery, they are at risk for intravascular volume depletion even prior to blood loss.

Hypothesis Ib: Because clinicians use pulse pressure variability, heart rate, systolic blood pressure, urine output, and blood loss to gauge need for ongoing resuscitation (either crystalloid, colloid, or blood), we suspect that more than half of subsequent fluid challenges will be given to infants who are fluid responsive (defined by a pre- and post-bolus ΔV_{Peak} of $> 10\%$).

Aim II: To determine the PPV, NPV, sensitivity, specificity, and optimal threshold for CRI, collapsibility index, pulse pressure variability, stroke volume variability, heart rate, systolic blood pressure, and mean arterial pressure as tools to predict fluid responsiveness using pre- and post-fluid challenge $\Delta V_{Peak} > 10\%$ to define fluid responders.

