4.2 Materials Necessary

1. Esophageal aortic Doppler (CardioQ-EDM) probe = 30 provided by Deltex Medical

Protocol #: 18-2513

PI: [name]

Version date: 07/01/2019

2. CardioQ-EDM monitor = 2 provided by Deltex Medical
3. Bedside Ultrasound = 2 machines are available in the operating room at all times
4. CipherOx CRI – Provided by Division of Pediatric Surgery

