4.9.1 CardioQ-EDM Details

- The Deltex Medical Doppler KDP72 probe is for use in patients aged 15 years or younger for up to 72 hours.
- The KDP probe is 28 in (72 cm) long and has maximum usage time which is defined on the probe packaging.
- It is only approved for ORAL placement into the esophagus of a single patient over 5.5 lb. (2.5 kg) in weight.
- The patient should be under full sedation or general anesthesia.
- The probe shaft has six depth markers visible through the transparent cover starting at 6 in (15 cm) through to 16 in (40 cm) incrementing in steps of 2 in (5 cm). These markers act as a guide to facilitate correct probe placement.
- Nasal placement of any probes in patients aged 15 years or younger is not approved nor is usage of the CardioQ-EDM for patients below 5.5 lb. (2.5 kg) in weight.

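### With about 30 evaluable children, the unpenalised adjusted logistic models in section 4.8 carry a material risk of separation in the first-bolus analysis, and the plan has no fallback

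*Combined protocol and SAP*

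**What the plan says.** Section 4.8 plans two logistic models for each of CI and CRI: simple ones with "no confounders and multiple logistic regression models including confounders". A covariate enters the adjusted model on its "univariate association with the gold standard (using a $p < 0.10$ threshold"; the number that may enter is not limited. The adjusted models then have a job to do: "These adjusted models will be used to verify thresholds for classification using CI and CRI". The thresholds so verified yield PPV, NPV, sensitivity and specificity, the outputs of Aim II.

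Hypothesis II (section 3) expects CRI and CI to reach an "approximate area under the receiver operating characteristic curve (AUROC) of 0.9". Hypothesis Ia expects that "approximately half of the cohort will be fluid responsive" at the bolus after induction. Section 5 plans one analysis of that first bolus and a second of all boluses.

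The supplied text gives no sample size. Section 4.2 lists "Esophageal aortic Doppler (CardioQ-EDM) probe = 30 provided by Deltex Medical", and section 4.9.1 says of the probe: "It is only approved for ORAL placement into the esophagus of a single patient over 5.5 lb. (2.5 kg) in weight". No supplied section says what happens if a model separates or fails to converge.

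**The concern.** Ordinary logistic regression has no finite maximum-likelihood estimate when some combination of the predictors splits responders from non-responders without overlap (complete separation), or with overlap only at the boundary (quasi-complete separation). Three features of the plan push towards this: a small number of children, an index expected to discriminate well, and covariates admitted because they happen to differ between the two groups.

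If the model separates, at least one coefficient and its standard error grow without limit, and the intervals and any cut-off read from fitted probabilities mean nothing. Under complete separation the fitted probabilities go to 0 or 1 and the adjusted AUC prints as 1.000. That figure describes the index and the screened covariates together in one small sample, yet it could be read as strong support for a device that the sponsor hopes may replace arterial lines. The risk also grows as the index gets better, so the check is most fragile when Hypothesis II is true.

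**Working it through.** The plan has no figure of its own to reproduce, so the rate was estimated by simulation.

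**Inputs from the documents**
- Children: 30, inferred from the probe supply. Fewer may be evaluable, because a displaced probe ends the study for that child (4.9), and abnormal IVC anatomy (4.3.2) or emergency use of the data (4.7) excludes the child.
- Responders: one half (Hypothesis Ia).
- Index AUC: 0.90 (Hypothesis II).
- Screen: p<0.10 by t-test or Fisher's exact test (4.8).
- Candidates: the Aim III table in section 5 lists 20, reading ventilation as a heading. Section 4.8 does not cite that table, so smaller pools were also tried.

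**Assumptions, not in the documents**
- A binormal index.
- Candidates split into 13-14 continuous and 6-7 binary items in the 20-item pool, and mutually independent except in the 14-item run.
- Where confounders are real, three of them differ by 0.6 SD between the groups.

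**Step 1: strength of the index.** AUC = Φ(d/√2), so d = √2 × z(0.90) = 1.414 × 1.2816 = 1.81 SD between the groups.

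**Step 2: covariates passing by chance.** With 20 unrelated candidates, 20 × 0.10 = 2 are expected to pass, and P(3 or more) = 32% for a binomial(20, 0.10). In the simulations about 1.7 passed on average. With 12 candidates, 12 × 0.10 = 1.2 are expected.

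**Step 3: test for separation.** In each simulated trial a linear program looked for a, b, not all zero, with a + b′x ≥ 0 for every responder and ≤ 0 for every non-responder. If all inequalities can be made strict, separation is complete.

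**Step 4: results, first-bolus analysis, one adjusted model.** Ranges are across runs with slightly different assumptions.

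| Setting | No true confounder | Three at 0.6 SD |
|---|---|---|
| N=30, 20 candidates | 14-18% | 31-35% |
| N=30, 14 candidates, some correlated | 10.6% | 25% |
| N=30, 12 candidates | 8-9% | 20-22% |
| N=25, 20 candidates | 29-31% | 46% |
| N=25, 12 candidates | about 17% | about 33% |
| N=40, 20 candidates | 4% | 14% |
| N=60, 20 candidates | 0.2-0.4% | 3% |
| N=30, 20 candidates, AUC 0.80 | 6-11% | 16% |
| N=30, 20 candidates, AUC 0.95 | 35% | not run |

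Monte Carlo error is about 1 to 2 points; for example, √(0.175 × 0.825 / 800) = 1.3 points. In the run that gave 17.5% at N=30, complete separation made up 14 points.

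**Step 5: what drives it.** The index alone separates in about 1% of trials at N=30 and 1-3% at N=25. With two fixed unrelated continuous covariates in place of the screen, the rate at N=30 is about 4%; with five, 24%. So the screened covariates are the cause, not the AUC of 0.9 by itself.

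**Step 6: two models.** CI and CRI share the screened covariates. At N=30, at least one of the two adjusted models separates in 26-27% of trials (none real) or 45% (three real) with 20 candidates, and in 12-14% or 31-33% with 12.

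**The case against.** The strongest reply has four parts.

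- **Sample size.** N=30 is a supply figure, not a stated sample size. Parts of the document were not available for review and may give one, and section 3's background cites 50-70 cases a year. At 60 independent children the problem nearly vanishes. This stands, and the point is conditional on about 30.
- **Candidate pool.** The Aim III table specifies multivariable linear regression and is not cited in 4.8. Before the first bolus, transfusion, fluid totals and vasopressor totals would mostly not vary. This also stands, and it is why the 12- and 14-candidate rows are shown. The risk shrinks but does not go away.
- **Frequency and consequence.** A reader might infer that the adjusted model will usually fail, or that no threshold could then be derived. The documents support neither. With no true confounder at N=30, more than 80% of trials give finite, though possibly overfitted, estimates. Section 4.8 uses the adjusted models to verify thresholds, not as their only source; it also plans index-only models, and section 5 already shows a CI cut-off of 15%. A raw CI or CRI cut-off and its sensitivity, specificity, PPV and NPV exist whether or not the adjusted model separates.
- **All boluses.** That analysis has at least as many records, so separation is less likely. This is fair, but boluses within a child are not independent, and no rate was computed for it.

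What the reply leaves untouched is that the verification step in 4.8 has a foreseeable failure and no stated handling.

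**Conclusion.** The point holds in a limited form. In the first-bolus analysis, with about 30 evaluable children, half responding and an index AUC of 0.9, each adjusted model separates completely or quasi-completely in roughly 8-18% of trials if no confounder is real (12 to 20 candidates), and in about 20-35% if three differ moderately. No passage fixes the confounder effects, so the second range is illustrative.

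Where separation occurs, the adjusted coefficients, their intervals and any threshold based on fitted probabilities are not finite or not informative, and the check on the thresholds tells the reader nothing. The Aim II classification results on the raw index survive. This is worth correcting because the remedy is cheap and an adjusted AUC of 1.000 would mislead; it does not invalidate the study.

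**What to change.** In section 4.8:

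1. Derive the CI and CRI classification thresholds from the index-only ROC curve, so that they do not depend on whether the adjusted model has a finite fit.
2. Fit the adjusted CI and CRI models by Firth's penalised likelihood with profile-likelihood intervals, and label them a secondary check.
3. Report for each adjusted model whether complete or quasi-complete separation occurred.

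A cap on the number of covariates would lower the risk further but is a matter of judgement and is not needed for this point. Firth's method keeps the estimates finite; it does not remove the optimism that comes from screening at p<0.10, so the adjusted AUC should still not be read as the accuracy of the index.

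The cost is a change of SAP wording. The method is available in both R and SAS, the software named in 4.8. Coefficients are slightly shrunk, and the adjusted AUC may look a little less favourable.
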